9.4. Deaths, Serious Adverse Events, and Other Significant Adverse Events

A serious adverse event is an AE that fulfills the following criteria:

- Is fatal (results in death);
- Is life-threatening (Note: the term "life-threatening" refers to an event in which the subject was at risk of death at the time of the event; it does not refer to an event that could hypothetically have caused death had it been more severe);
- Requires inpatient hospitalization or prolongation of existing hospitalization (hospitalization is defined as an inpatient admission, regardless of length of stay);
- Results in persistent or significant disability/incapacity (a substantial disruption of the subject's ability to conduct normal life functions);
- Is a congenital anomaly/birth defect; or
- Constitutes an important medical event that may jeopardize the subject or may require medical or surgical intervention to prevent one of the other outcomes listed above.

Serious adverse events will be summarized according to Section 9.3.

By-subject listings will be provided for any deaths, serious adverse events, and AEs leading to discontinuation of treatment. TEAEs that result in dose interruption or reduction will also be identified.

9.5. Clinical Laboratory Evaluation

Clinical laboratory samples should be collected at the beginning of each clinic visit and just prior to a dose on all Study Visit Days and will be processed by a central laboratory. In the event a subject is unable to attend an in-clinic visit due to COVID-19, clinical laboratory blood draws may be performed by a Home Health Care agency or a local laboratory.

Clinical laboratory variables will be presented in 3 ways. First, the mean change from baseline to each scheduled assessment will be summarized descriptively by dosing regimen for each

Sun Pharmaceutical Industries, Inc.
Statistical Analysis Plan – CP543.5002

clinical laboratory variable specified in this protocol. Change from baseline will be summarized separately for the “pre-zero” baseline and the CP543.5002 study baseline (see Section 6.2). Values will only be included if the subject had both a baseline and post-baseline value for that parameter.

Second, treatment-emergent potentially clinically significant (PCS) laboratory values will be identified. Potentially clinically significant values are defined as those that meet Grade 3 or Grade 4 toxicity criteria from the common terminology criteria for adverse events (CTCAE) criteria (or Grade 2 or higher for platelets). Laboratory values will be graded using CTCAE version 5.0, for those values included. CTCAE grades will be based solely on numeric results and without regard to other symptoms based on clinical judgment. For laboratory parameters whose CTCAE grading is independent of baseline criteria, treatment-emergent PCS laboratory values are those in which the CP543.5002 study baseline value is not PCS and the post-baseline value is PCS. For laboratory parameters whose CTCAE grading is dependent upon baseline criteria, any post-baseline grading of Grade 3 or Grade 4 (or 2 or higher in the case of platelets) will be considered treatment-emergent, and values will only be included if the subject had both a baseline and post-baseline value for that parameter. The number and percentage of subjects with treatment-emergent PCS laboratory values will be summarized by treatment group and overall for each clinical laboratory variable, separately for the “pre-dose” baseline and the CP543.5002 study baseline. Results will be presented by post-baseline visit and overall; for this analysis, the visit with the highest CTCAE grade value within an analysis window will be selected.

Third, laboratory values which are TEAEs that result in dose interruption will be recorded as TEAEs. These analyses are described in Section 9.3.

These analyses will be performed for serum chemistry results, hematology results, and lipid results (where lipid tests include total cholesterol, low-density lipoprotein, high-density lipoprotein, triglycerides). Laboratory results will also be listed. Central laboratory reference ranges for each clinical laboratory parameter will also be summarized in a data listing.

Pregnancy test results will be listed only.

Laboratory results for subjects who experience the hematologic thresholds in Table 3 will also be listed.

Table 3: Selected Hematologic Thresholds for Dose Interruption

Neutrophil Count	< 0.5 x 10 ⁹ /L
	≥ 0.5 x 10 ⁹ /L and < 1 x 10 ⁹ /L
Hemoglobin Level	Female: < 10 g/dL
	Male: < 11.5 g/dL
Platelet Count	< 75 x 10 ⁹ /L
	> 750 x 10 ⁹ /L

The mean and standard error for key hematology parameters (Alanine aminotransferase [ALT], neutrophils, platelets, and hemoglobin) and other laboratory parameters (lymphocyte count, reticulocyte count, cholesterol, HDL, LDL, creatinine, creatine kinase, aspartate aminotransferase [AST], alkaline phosphatase, amylase, lipase, and triglycerides) may be summarized graphically by visit and treatment group.

Box Plots

Box plots for hemoglobin, platelets, neutrophils, lipase, triglycerides, and CPK may be produced visit and treatment group as a means of identifying outliers. The median will be presented as a line within the box, with the 25th and 75th percentiles defining the edges of the box. The mean will be plotted as a circle. The interquartile range (IQR) will be defined as the difference between the 25th and 75th percentile. The whiskers will extend 1.5 times the IQR from the top and bottom of the box. If the data do not extend to the end of the whiskers, then the whiskers will extend to the minimum and maximum data values. If there are values which fall above or below the end of the whiskers, they will be plotted as dots.

Potential Hy's Law

The number and percentages of subjects with at least 1 post-baseline value of ALP, ALT, AST and/or total bilirubin will be tabulated, based on the cut-offs provided in [Table 4](#) below.

Table 4: Elevated Liver Chemistry Criteria

Clinical Laboratory Parameter	Category
ALT	$\geq 3 \times \text{ULN}$; $\geq 5 \times \text{ULN}$
AST	$\geq 3 \times \text{ULN}$; $\geq 5 \times \text{ULN}$
ALT or AST	$\geq 3 \times \text{ULN}$; $\geq 5 \times \text{ULN}$
ALP	$\geq 1.5 \times \text{ULN}$; $\geq 2 \times \text{ULN}$
Total bilirubin	$\geq 1.5 \times \text{ULN}$; $\geq 2 \times \text{ULN}$; $\geq 3 \times \text{ULN}$
Concurrent total bilirubin elevation with ALT elevation ^[1]	(ALT $\geq 3 \times \text{ULN}$) and (total bilirubin $\geq 2 \times \text{ULN}$)
Concurrent total bilirubin elevation with ALT or AST elevation ^[1]	(ALT or AST $\geq 3 \times \text{ULN}$) and (total bilirubin $\geq 2 \times \text{ULN}$)
Concurrent total bilirubin elevation with ALT or AST elevation and ALP $< 2 \times \text{ULN}$ ^[1] ("potential Hy's law cases")	(ALT or AST $\geq 3 \times \text{ULN}$) and ALP $< 2 \times \text{ULN}$ and (total bilirubin $\geq 2 \times \text{ULN}$)

ALP = alkaline phosphatase; ALT = alanine aminotransferase; AST = aspartate aminotransferase; ULN = upper limit of normal

[1] Concurrent means on the same date.

Potential Hy's law cases (based on the recommendation in "Guidance for Industry Drug-Induced Liver Injury: Premarketing Clinical Evaluation") will be identified as subjects with ALT or AST

≥ 3 x upper limit of normal (ULN) , ALP < 2 x ULN, and total bilirubin ≥ 2 x ULN on the same date, as noted above.

To assess cases potentially meeting requirements for Hy's Law, an evaluation of drug-induced serious hepatotoxicity (eDISH) plots of bilirubin against peak ALT will be generated by treatment group, as described by Watkins et al (2008). This plot will be reproduced for peak AST vs. peak total bilirubin, as well as for the greater of peak AST and peak ALT vs. peak total bilirubin.

Potential drug-induced liver injuries will also be presented in a listing, including all relevant laboratory measurements displayed by visit. One listing will show all subjects with ALT or AST ≥ 3 x ULN and total bilirubin ≥ 2 x ULN at the same visit. A second listing will show all subjects with ALT or AST ≥ 5 x ULN.

Graphical representations of the liver function tests (ALP, ALT, AST and total bilirubin) over time, including drug exposure times, will be produced for subjects with possible drug induced liver injury.

Additional exploratory analyses of laboratory evaluations may be conducted based on data reviews.

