## 7.3. Patient Withdrawal Criteria

All patients are free to withdraw from participation in the study at any time, for any reason, and without prejudice. The Investigator must withdraw any patient from the study if the patient requests to stop participating in the study. The Investigator, Sponsor, or its designee may remove a patient from the study at any time and for any reason. In addition, patients must be withdrawn if they:

- Have a prior history of thrombotic event(s);
- Experience a thromboembolic event;
- Experience an intolerable adverse event, including but not limited to bone marrow related events characterized by protocol specified hematologic abnormalities, or a  $\geq$  Grade 3 cardiac event, or a  $\geq$  Grade 4 (other) adverse event (CTCAE v5.0 criteria) considered possibly related to study drug. Because laboratory abnormalities can occasionally occur that do not in themselves pose an unacceptable risk to subject safety (e.g., CK elevations with exercise, laboratory errors or artifacts), the occurrence of a  $\geq$  Grade 4 laboratory abnormality, or any laboratory abnormality of concern to the Investigator, will be discussed with the Medical Monitor and a determination will be made, based on a reassessment of risk-benefit for the subject, whether the subject should discontinue randomized treatment. Documentation on the determination will be maintained in the study files;
- Require a medication that is prohibited by the protocol. However, under certain circumstances, and in consultation with the Medical Monitor, short-term use of a

prohibited medication may not necessitate withdrawal when its use is unlikely to unfavorably alter the risk-benefit of subject participation or confound the study endpoints;

- Experience an adverse event of progressive multifocal leukoencephalopathy (PML) or skin cancer which are rare but potential risks of the drug;
- Do not follow guidelines specified in the protocol (i.e., is noncompliant with protocol procedures or study treatment administration);
- In the opinion of the Investigator, have any medically appropriate reason or significant protocol violation;
- Become pregnant;
- Have a serious adverse event associated with a SARS-CoV-2 infection;
- Are lost to follow up;
- Are, in the judgement of the Investigator, not exhibiting clear benefit following one full year of active treatment with CTP-543;

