#### **11.2.3.2. Clinical Laboratory**

Clinical laboratory variables will be presented 3 ways. First, change from Baseline to each scheduled assessment will be summarized descriptively. Baseline will be defined as the laboratory value obtained before the first dose of study drug on Day 1.

Second, treatment-emergent potentially clinically significant (PCS) laboratory values will be identified. Potentially clinically significant values are defined as those that meet Grade 3 or Grade 4 toxicity criteria from the CTCAE criteria. Treatment-emergent PCS laboratory values are those in which the Baseline value is not PCS and the post-baseline value is PCS.

Third, treatment-emergent adverse events that result in dose interruption will also be identified.

The mean change from Baseline to each scheduled assessment will be summarized descriptively by dosing regimen for each clinical laboratory variable specified in this protocol.

The number and percentage of patients with Abnormal, clinically significant laboratory values (per Investigator judgement) and the number and percentage of patients with treatment-emergent PCS laboratory values will be summarized by dosing regimen for each clinical laboratory variable.

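### For laboratory parameters graded independently of baseline, the SAP 9.5 study-baseline table of treatment-emergent PCS values leaves out worsening within the PCS range, such as Grade 3 to Grade 4

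*SAP*

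**What the plan says.** SAP Section 9.5 sets the PCS threshold: "Potentially clinically significant values are defined as those that meet Grade 3 or Grade 4 toxicity criteria from the common terminology criteria for adverse events", with a lower cut for platelets ("or Grade 2 or higher for platelets"). It then gives two rules for when a PCS value is treatment-emergent.

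- **Grading independent of baseline.** The rule opens "For laboratory parameters whose CTCAE grading is independent of baseline criteria" and continues: "treatment-emergent PCS laboratory values are those in which the CP543.5002 study baseline value is not PCS and the post-baseline value is PCS".
- **Grading dependent on baseline.** Here "any post-baseline grading of Grade 3 or Grade 4 (or 2 or higher in the case of platelets) will be considered treatment-emergent", provided that both a baseline and a post-baseline value exist.

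The counts are to be given "separately for the “pre-dose” baseline and the CP543.5002 study baseline". The first of these names is not defined. SAP Section 6.2 defines a pre-zero baseline (the last value before the first active dose in either study) and a study baseline (the last value before the first dose in this study), so pre-zero is presumably meant.

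Protocol Section 11.2.3.2 has one rule without the split: "Treatment-emergent PCS laboratory values are those in which the Baseline value is not PCS and the post-baseline value is PCS".

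Under SAP Section 4 the default denominator is the whole population being summarised. SAP 9.5 plans no laboratory grade-shift table and no separate Grade 4 row. SAP 9.6.1 does plan baseline-to-worst-grade shift tables, for systolic and diastolic blood pressure.

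**The concern.** Under the first rule, treatment-emergent means crossing one line, from not PCS to PCS. All grades above the line are pooled, so a move from Grade 3 to Grade 4 crosses nothing and is not counted. For platelets the line is one grade lower, so Grade 2 to 3, 2 to 4 and 3 to 4 all drop out.

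This matters more in a roll-over study than in a trial of untreated patients. The study baseline is the last visit of the parent trial, so for patients who had active drug it follows 24 weeks of exposure. A Grade 3 value on that day may already have arisen on treatment, and further deterioration is something a long-term safety study should be able to show. Exclusion criterion 4 addresses haematology only, and no entry criterion sets a grade limit for chemistry or lipids, so PCS values at entry are possible.

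Grade 4 also has a role of its own in the protocol: under Section 7.3 the occurrence of a "Grade 4 laboratory abnormality, or any laboratory abnormality of concern to the Investigator, will be discussed with the Medical Monitor", with a decision on whether treatment should stop. A summary that neither counts progression to Grade 4 nor separates Grade 4 from Grade 3 is less useful than it could be.

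**Working it through.** The documents state no figure for this point, so there is none to reproduce. The check applies the two SAP rules to every possible worsening.

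**Inputs.** Grades run from 0 to 4. The PCS cut c is 3, or 2 for platelets (SAP 9.5). Let b be the baseline grade and p the post-baseline grade. A relevant worsening has p > b and p ≥ c.

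- Independent rule: counted if b < c and p ≥ c.
- Dependent rule: counted if p ≥ c.

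**Number of relevant worsenings.**

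- c = 3: three ways to reach Grade 3 (from 0, 1, 2) and four to reach Grade 4 (from 0, 1, 2, 3). 3 + 4 = 7.
- c = 2: two ways to reach Grade 2, three to reach Grade 3, four to reach Grade 4. 2 + 3 + 4 = 9.

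| Rule | Non-platelet, missed | Platelet cut, missed |
|---|---|---|
| Independent of baseline | 1 of 7 (3→4) | 3 of 9 (2→3, 2→4, 3→4) |
| Dependent on baseline | 0 of 7 | 0 of 9 |
| Proposed: p ≥ c and p > b | 0 of 7 | 0 of 9 |

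These are counts of transition types, not proportions of patients.

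**Two baselines.** Take a non-platelet parameter at Grade 3 at study baseline and Grade 4 later, and assume that the same rule is applied to the pre-zero value. The SAP text of the rule names only the study baseline.

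| Pre-zero grade | Study-baseline table | Pre-zero table |
|---|---|---|
| 0, 1 or 2 | not counted | counted |
| 3 or 4 | not counted | not counted |

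A patient who had placebo in the parent trial takes the first active dose in this study. By SAP 6.2 the pre-zero and study baselines are then the same observation, so the case falls in the second row and is missed in both tables. In the first row the case is counted, but as PCS only; the table does not show that it reached Grade 4.

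**Effect of the proposed rule on present counts.** If b < c and p ≥ c, then p > b. Every case counted now under the independent rule is still counted, so counts for those parameters can stay the same or rise, but not fall.

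**The case against.** Several points on the other side stand.

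- **Not every case is lost.** A reader might infer that Grade 3 to 4 worsening is never counted, whichever baseline is used. The documents do not support that. A patient at Grade 0 to 2 before any active drug, Grade 3 at entry and Grade 4 later is counted against the pre-zero baseline, and that is the pattern most suggestive of a drug effect. Baseline-dependent parameters are not affected at all.
- **The two rules are not shown to contradict each other.** Where the grade is already relative to baseline, requiring a non-PCS baseline as well could adjust twice. That rule can stand.
- **Other outputs overlap.** SAP 9.5 tabulates ALT, AST, ALP and bilirubin on any post-baseline value. Laboratory abnormalities judged clinically significant, or leading to discontinuation, become adverse events (Protocol 9.2 and 10.1) and are summarised. All laboratory results are listed. These routes are partial: the liver table covers four tests by multiples of the upper limit of normal, adverse event status mainly rests on investigator judgement, SAP 9.3 pools severity at Grade 3 or above, and listings are not counts.
- **Patient safety review does not depend on this table.** A reader might infer that the rule weakens the Grade 4 review in Protocol 7.3. It does not. That review is done per patient during the study and also covers any laboratory abnormality that concerns the investigator.
- **The rule was prespecified, the study is descriptive**, and exclusion criterion 4 should remove some PCS haematology values at entry.

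A reader might also infer that a change from PCS-low to PCS-high is lost. The SAP does not say whether PCS status is assessed by direction, and the table shells are not in the documents, so this cannot be settled.

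**Conclusion.** The point holds within a limited scope. For baseline-independent parameters, the study-baseline treatment-emergent PCS summary omits Grade 3 to 4 (1 of 7 worsening types) and, at the platelet cut, Grade 2 to 3, 2 to 4 and 3 to 4 (3 of 9). The pre-zero summary recovers the case only where the pre-zero value was not PCS, and then without showing Grade 4. This rests on two assumptions: that the undefined baseline name in 9.5 means pre-zero, and that the same rule is applied to it.

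The number of patients cannot be derived. The documents give no baseline grade counts, and which parameters fall under each rule depends on CTCAE v5.0, which they do not reproduce. It would be tempting to assume that 1% to 3% of 300 patients enter at Grade 3 in some chemistry or lipid test, giving 3 to 9 patients. Both inputs would be guesses. The figure would also cover all the chemistry and lipid tests together, not any one of them, and only those who later worsened would be miscounted. It should not be quoted as the size of the problem.

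This is a reporting gap in one safety table and worth closing because the remedy is cheap. It is not evidence that Grade 4 events would go unnoticed.

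**What to change.** In SAP 9.5, for parameters graded independently of baseline, define treatment-emergent PCS as a post-baseline PCS grade higher than the baseline grade in the same direction (low or high). State that this applies to each of the two baselines, and replace the undefined baseline name with pre-zero. Leave the rule for baseline-dependent parameters as it is: requiring a grade increase there could remove cases that the SAP now counts.

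Show Grade 3 and Grade 4 as separate rows, with Grade 2 as well for platelets. Alternatively, add a baseline-to-worst-grade shift table in the format that SAP 9.6.1 uses for blood pressure.

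Record the change from Protocol 11.2.3.2 in SAP Section 12. That section now quotes a protocol sentence covering both the investigator-judged summary and the PCS summary and says that the analysis is removed, while 9.5 keeps the PCS part. It should say which part is dropped.

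The cost is a few sentences in the SAP and a small programming change. No new data are needed and no clinical rule changes. Emergent counts may rise slightly.

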6.2. Demographic and Other Baseline Characteristics

Demographic characteristics (i.e. sex, ethnic origin, race, and age) will be collected at the Day 1 visit, which will occur on the same day as their last visit in the preceding clinical trial, and detailed on the eCRF. Age will be reported as collected in the eCRF for the CP543.5002 study. Baseline body mass index (BMI) will be calculated based on data from the preceding clinical trial, using the weight from the last visit and the height. Demographic characteristics will be summarized using descriptive statistics for all subjects in the Enrolled Population, and separately for all subjects in the Safety Population.

Sun Pharmaceutical Industries, Inc.
Statistical Analysis Plan – CP543.5002

Baseline characteristics will be summarized for both the “pre-zero” baseline and the CP543.5002 study baseline using descriptive statistics for the Safety Population by treatment group and overall and will include the following:

- baseline total SALT score
- baseline alopecia areata classification: scalp hair loss (SALT <50); partial scalp hair loss (SALT \geq 50 and < 95); complete or near-complete scalp hair loss (SALT \geq 95)
- whether the subject has experienced any past and/or concomitant diseases, conditions, exposures to serious infections, or past surgeries (as collected in CP543.3001 and CP543.3002)

The “pre-zero” baseline is defined as the last observation obtained prior to first dose of active drug in either CP543.5002 or the qualifying study. “CP543.5002 study baseline” is defined as the last observation prior to first dose in CP543.5002.

Other co-morbidities may be identified and included as baseline characteristics.

All demographics characteristics will be listed within a by-subject data listing for all enrolled subjects.

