9.6.3. Other Safety Measures

9.6.3.1. 12-Lead Electrocardiogram

Twelve-lead ECGs will be performed at Week 52, Week 108 (for responders only), and/or the Early Termination Visit. Individual parameters including heart rate, PR, QT, QTcF (Frederica's correction), QRS, RR intervals will be collected. If a subject is unable to attend an in-person clinic visit due to COVID-19, a 12-lead ECG may not be performed. Missed assessments will be recorded in the eCRF as due to COVID-19.

The mean and mean change from baseline to each scheduled assessment will be summarized descriptively by treatment group and overall for each 12-lead ECG variable specified in the protocol. Change from baseline will be summarized separately for the “pre-zero” baseline and the CP543.5002 study baseline (see Section 6.2); only subjects who have both a baseline and at least 1 post-baseline assessment will be included. Clinically significant ECG results will be identified based on the criteria in Table 5, and will be summarized descriptively by treatment group and overall, separately for each baseline definition. Clinically significant ECG results will

Sun Pharmaceutical Industries, Inc.
Statistical Analysis Plan – CP543.5002

be identified based on the criteria below. For each ECG parameter, the number and percentage of subjects with at least 1 treatment-emergent notable value will be tabulated overall, using the worst post-baseline value. The number and percentage will be summarized separately for the “pre-zero” baseline and the CP543.5002 study baseline (see Section 6.2). To be defined as treatment-emergent, the criteria should be met after first dose of study drug (as applicable to each baseline definition) and not met at baseline. Clinically significant ECG results for subjects who meet the criteria after first dose of study drug and are missing their baseline value will conservatively be counted as treatment-emergent.

Table 5: Clinically Significant ECG Criteria

ECG Parameter	Criteria
QTcF	Post-baseline >450 msec Post-baseline >480 msec Post-baseline \geq 500 msec Post-baseline >450 msec and \leq 480 msec Post-baseline >480 msec and \leq 500 msec Post-baseline increase >30 msec Post-baseline increase >60 msec Post-baseline increase >30 msec resulting in a post-baseline >450 msec Post-baseline increase >30 msec resulting in a post-baseline >480 msec Post-baseline increase >30 msec resulting in a post-baseline \geq 500 msec

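### SAP 9.5 orders treatment-emergent PCS laboratory counts on two baselines but, for baseline-independent CTCAE grades, defines emergence against only one of them, so the second table read literally repeats the first

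*SAP*

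**What the plan says.** SAP 6.2 defines two baselines. The *pre-zero* "baseline is defined as the last observation obtained prior to first dose of active drug in either CP543.5002 or the qualifying study". The CP543.5002 study baseline "is defined as the last observation prior to first dose in CP543.5002". SAP Section 4 uses the same pair for every change-from-baseline display.

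SAP 9.5 defines PCS as CTCAE Grade 3 or 4, or Grade 2 and above for platelets. It then gives two emergence rules:

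- Where the CTCAE grade does not depend on baseline: "treatment-emergent PCS laboratory values are those in which the CP543.5002 study baseline value is not PCS and the post-baseline value is PCS".
- Where the grade does depend on baseline: "any post-baseline grading of Grade 3 or Grade 4 (or 2 or higher in the case of platelets) will be considered treatment-emergent".

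The paragraph closes by asking for the emergent counts "separately for the “pre-dose” baseline and the CP543.5002 study baseline". The term *pre-dose* baseline is not defined. For laboratory change from baseline, earlier in the same section, the wording is different: "Change from baseline will be summarized separately for the “pre-zero” baseline and the CP543.5002 study baseline (see Section 6.2").

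The ECG section (SAP 9.6.3.1) also tabulates on two baselines, and there the rule follows the baseline: "To be defined as treatment-emergent, the criteria should be met after first dose of study drug (as applicable to each baseline definition"), with the further condition that the criterion was not met at that baseline.

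Protocol 11.2.3.2 has one laboratory baseline, the value before the first dose on Day 1, and so has no second table.

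**The concern.** For a patient who took 8 mg or 12 mg BID in the parent trial, the CP543.5002 baseline is an on-drug value carried over from the last parent-trial visit (Protocol Table 1, footnote 2; SAP Section 4). The second baseline lets the reader see change since the patient was last free of active drug. If emergence in the second table is still judged against the CP543.5002 baseline, the table cannot do that for baseline-independent parameters. It would carry a label that does not match its content, in a study whose first objective is long-term safety.

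Nothing else in the documents settles the matter. SAP Section 4 lets section-specific rules override the general conventions, SAP Section 2 gives the SAP primacy over the protocol, and the protocol had only the one baseline.

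**Working it through.** The plan states no figure to reproduce, and the check needs no arithmetic beyond enumeration. It sets the literal rule beside the same rule anchored to pre-zero and runs through every pattern.

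**Inputs**
- Z: PCS at the pre-zero baseline (SAP 6.2).
- B: PCS at the CP543.5002 baseline (SAP 6.2).
- P: PCS at a post-baseline CP543.5002 visit (SAP 9.5; windows in SAP Table 2).
- Rule A, the literal text of SAP 9.5 for baseline-independent grades: emergent if B = No and P = Yes.
- Rule B, the same rule anchored to pre-zero: emergent if Z = No and P = Yes.

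| Z | B | P | Rule A | Rule B | Agree? |
|---|---|---|---|---|---|
| No | No | No | no | no | yes |
| No | No | Yes | emergent | emergent | yes |
| No | Yes | No | no | no | yes |
| No | Yes | Yes | no | emergent | **no** |
| Yes | No | No | no | no | yes |
| Yes | No | Yes | emergent | no | **no** |
| Yes | Yes | No | no | no | yes |
| Yes | Yes | Yes | no | no | yes |

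**Results**
1. Rule A does not involve Z. If it governs both tables, they are identical for these parameters and the second adds nothing.
2. Two of the eight patterns are misclassified in a table labelled as pre-zero, and they err in opposite directions. (No, Yes, Yes), where the abnormality arose on parent-trial drug and persists, is missed. (Yes, No, Yes), where it was present before any active drug and returned, is counted as emergent.
3. For former placebo patients the first active dose is the first CP543.5002 dose, so Z and B are the same observation. Only patterns with Z = B can occur, and Rules A and B agree on all of them. The problem is confined to patients on active drug in the parent trial.
4. For baseline-dependent grades the SAP does not require a non-PCS baseline, so Rule A does not apply to them.

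**Comparison within the SAP.** Three safety displays use emergence criteria of this kind. ECG orders two baselines and ties emergence to each. Notable heart rate (SAP 9.6.1) footnotes the CP543.5002 baseline and orders no second table. Only the laboratory section names one baseline in the rule and orders two tables.

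**Section 12.** It quotes the protocol sentence that covers both the investigator-judged abnormalities and the treatment-emergent PCS values, then says the SAP drops the analysis because of the CRF design. SAP 9.5 keeps the PCS half. Since 9.5 grades on numeric results alone, the stated reason seems to fit only the investigator-judged half, but the text does not say so.

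**The case against.** The strongest reply is that the literal reading is not the natural one. Asking for separate counts by baseline makes sense only if emergence is judged against each, and *pre-dose* looks like a slip for *pre-zero*. A programmer who reads it that way will produce the right second table. The table shells attached to the SAP might settle it, but they are not available here. This stands as far as it goes: the text contradicts itself, so the misclassification is possible, not certain. It does not remove the need to state the rule.

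A second reply is that the values remain visible. All laboratory results are listed, patients crossing hematologic thresholds are listed separately, the liver table counts any post-baseline value, and mean change from pre-zero is summarised. Protocol exclusion criterion 4 keeps out patients whose hematology met the withholding criteria and has not recovered. Cross-study safety goes to a separate ISS plan. These points limit the consequence but do not restore the count. Listings give no incidence, the threshold listing and the exclusion criterion cover hematology only, and the liver table covers liver tests only. Other chemistry and lipids are left without an equivalent count. The adverse event tables do not fill the gap either: SAP 9.3 treats an event starting before the first CP543.5002 dose as pre-treatment, so an abnormality that merely persists is not a TEAE.

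A reader might infer that laboratory toxicity arising in the parent trial can never be counted as emergent. The documents do not support that. The baseline-dependent rule can count a persisting abnormality, and one that resolved by OLE baseline and then recurred is counted under Rule A. Nor can platelets safely serve as an example of lost cases, because the platelet grade threshold also appears inside the baseline-dependent rule.

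**Conclusion.** The point holds as a contradiction within one paragraph of SAP 9.5, limited to parameters with baseline-independent CTCAE grades and to patients on active drug in the parent trial. On the literal reading, the second table duplicates the first and misclassifies two of the eight patterns, one by omission and one by false inclusion. This is a stated rule that gives the wrong content for a planned safety table, so it is more than missing detail.

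The size in patients cannot be computed, because the documents do not say how many were PCS at either baseline. It is probably small: an affected patient must have had a Grade 3 or 4 value at one of the two baselines and again during the OLE. The study is descriptive, so no test or error rate is involved. The conclusion assumes that *pre-dose* means *pre-zero* and that post-baseline means CP543.5002 visits. It should be corrected before the tables are programmed, but it does not threaten the study.

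A reader might also infer that the second table ought to include abnormalities that arose and resolved within the parent trial. The SAP gives no basis for that: its windows start at the CP543.5002 baseline and its laboratory columns are defined by OLE dose, so parent-trial visits have neither an analysis visit nor a column.

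**What to change.** 1. In SAP 9.5, replace *pre-dose* with *pre-zero*, with a pointer to Section 6.2.
2. For baseline-independent grades, define treatment-emergent PCS in each table as not PCS at the baseline in question and PCS at a post-baseline CP543.5002 assessment, parallel to the ECG rule in 9.6.3.1. This adds the persisting cases to the pre-zero table and removes the recurrent ones; neither change affects the CP543.5002 table.
3. State that post-baseline means OLE visits in both tables, unless parent-trial visits are explicitly given windows and columns.
4. In SAP Section 12, say which half of the quoted protocol sentence is withdrawn, so that it agrees with 9.5.

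The cost is a sentence or two in 9.5, a clarification in Section 12 and one programming parameter for the baseline. No new data are needed.
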